3.3 Up-Dosing

Subjects will receive IP starting at a dose of 3 mg once daily and will gradually escalate every 2 weeks to a maximum of 300 mg once daily, according to the Up-Dosing Schedule ([Table 2](#)). All first escalation doses will be administered under direct observation in the clinical research center (CRC) or other monitored setting (unless required by a specific institution, no distinction will be drawn between an investigational site, study center office, clinic, or CRC, provided the requirements for monitoring and emergency intervention are met by the facility). Subsequent doses will be dispensed to the parent/guardian and administered at home. Doses may be adjusted for tolerability or inter-current illness by the Investigator, except no down-dosing below 3 mg/day is allowed. The allowed dose levels are shown in [Table 2](#). Up-dosing may thereby be extended to a maximum of 40 weeks in order to reach 300 mg and should not exceed this period.

Subjects unable to escalate to 300 mg within 40 weeks will be considered escalation failures. Subjects able to escalate to 300 mg will continue taking the 300 mg dose for an additional 2 weeks to ensure tolerability prior to exiting ARC007. If the subject is unable to tolerate the 300 mg dose for the 2-week period, dosing may continue up to a maximum of 48 weeks after Day 1 to ensure tolerability prior to exiting the study.

Table 2: Up-Dosing Schedule

Up-Dosing Schedule			
Dose Number	Investigational Product Dose, mg	Interval (weeks)	Percent Increase from Previous Dose
1	3	2 ^a	n/a
2	6	2	100
3	12	2	100
4	20	2	67
5	40	2	100
6	80	2	100
7	120	2	50
8	160	2	33
9	200	2	25
10	240	2	20
11	300	2 ^b	25

^a Interval includes Day 2 of Initial Escalation.

^b If the subject is unable to tolerate the 300 mg dose for the 2-week period, dosing may continue up to a maximum of 48 weeks after Day 1 to ensure tolerability prior to exiting the study.

3.4 Treatment Unblinding and Rollover to Studies ARC011 and ARC008

The treatment assignment for each subject will be unblinded after all exit visit procedures are completed and all major data queries for the subject have been resolved. For subjects participating in follow-on studies, both follow-on protocols must be activated at the study site before subjects can complete all of the exit procedures.

Subjects who received AR101 and completed ARC007 will have the option to participate in the ARC011 study. The ARC011 study is an open-label safety extension study of ARC007 to evaluate the safety and tolerability of 300 mg/d maintenance dosing for up to 6 months. After completing Study ARC011, subjects will be able to proceed to ARC008 for further maintenance dosing.

Subjects who received active treatment but did not reach 300 mg/d within 40 weeks or were unable to tolerate 300 mg daily for 2 weeks by 48 weeks after Day 1 will not be eligible for enrollment in ARC011 or ARC008.

Subjects who received placebo and completed ARC007 will be offered up-dosing and maintenance treatment with AR101 in the ARC008 study. In ARC008, these subjects will

undergo an escalation schedule identical to that for active subjects in the ARC007 study and then continue on maintenance dosing at 300 mg/d.

All subjects who enter ARC008 will be allowed to continue receiving AR101 until it becomes commercially available or the development program is terminated.

4. SELECTION AND WITHDRAWAL OF SUBJECTS

4.1 Inclusion Criteria

Subjects who meet all of the following criteria are eligible:

1. Age 4 to 17 years, inclusive
2. A history of physician-diagnosed IgE-mediated peanut allergy that includes the onset of characteristic allergic signs and symptoms within two hours of known oral exposure to peanut or a peanut-containing food. While IgE-mediated reactions have varied presentations, in general characteristic allergic signs and symptoms are objective and affect the target organs of the skin, GI tract, upper and/or lower respiratory tract, cardiovascular system, or a combination ([Appendix 2](#))
3. Mean peanut wheal diameter on SPT of ≥ 8 mm greater than the negative saline control at Screening
4. Serum IgE to peanut of ≥ 14 kU/L at Screening
5. Written informed consent from the subject's parent/guardian
6. Written assent from the subject as appropriate (eg, above the age of 7 years or the applicable age per local regulatory requirements)
7. Use of effective birth control method in sexually active females of childbearing potential

4.2 Exclusion Criteria

1. Subjects in whom the clinical diagnosis of peanut allergy is uncertain
2. History of cardiovascular disease, including uncontrolled or inadequately controlled hypertension (see Section [5.10](#))
3. Use of beta-blockers, angiotensin-converting enzyme (ACE) inhibitors, angiotensin-receptor blockers (ARBs), calcium channel blockers, or tricyclic antidepressants (see Section [5.10](#))
4. History of severe or life-threatening episode of anaphylaxis or anaphylactic shock within 60 days of screening
5. History of EoE, other eosinophilic GI disease, chronic, recurrent, or severe gastroesophageal reflux disease (GERD), symptoms of dysphagia (eg, difficulty swallowing, food “getting stuck”), or recurrent GI symptoms of undiagnosed etiology
6. History of a mast cell disorder, including mastocytosis, urticaria pigmentosa, chronic idiopathic or chronic physical urticaria beyond simple dermatographism (eg, cold urticaria, cholinergic urticaria), and hereditary or idiopathic angioedema

7. Severe persistent asthma (2007 National Heart, Lung, and Blood Institute [NHLBI] Criteria Steps 5 or 6, see [Appendix 3](#))
8. Mild or moderate persistent asthma (2007 NHLBI Criteria Steps 1 to 4), if uncontrolled or difficult to control as defined by any of the following:
 - a. Forced expiratory volume in 1 second (FEV₁) < 80% of predicted, with or without controller medications (only for age 6 years or greater and able to do spirometry); or
 - b. Inhaled corticosteroid (ICS) dosing of > 500 mcg daily fluticasone (or equivalent ICSs based on NHLBI dosing chart); or
 - c. One hospitalization in the past year prior to screening for asthma; or
 - d. Emergency room (ER) visit for asthma within 6 months prior to screening
9. History of high-dose corticosteroid use (eg, 1 to 2 mg/kg of prednisone or the equivalent for > 3 days) by any route of administration in any of the following manners:
 - a. History of daily steroid dosing for > 1 month during the past year; or
 - b. 1 steroid course in the past 3 months; or
 - c. > 2 steroid courses in the past year ≥ 1 week in duration
10. History of chronic disease (other than asthma, atopic dermatitis, or allergic rhinitis) that is, or is at significant risk of becoming, unstable or requiring a change in chronic therapeutic regimen
11. Inability to discontinue antihistamines 5 half-lives before the screening SPT and initial day of escalation
12. Lack of an available palatable vehicle food to which the subject is not additionally allergic
13. Hypersensitivity to epinephrine or any of the excipients in the epinephrine auto-injector
14. Use of omalizumab or any other monoclonal antibody therapy within the 6 months prior to screening or any current immunomodulatory therapy besides aeroallergen or venom immunotherapy or corticosteroids (see also Section [5.10](#))
15. Having received at least one dose of AR101 in a previous Aimmune or Allergen Research Corporation study
16. Use of other forms of peanut immunotherapy (eg, oral, sublingual, epicutaneous) within 6 months prior to screening
17. Participation in another clinical trial within 30 days or 5 half-lives of the IP, whichever is longer, prior to randomization
18. Concurrent administration of build-up phase of immunotherapy to another allergen (ie, subject has not reached maintenance dosing)
19. Pregnancy or lactation
20. Having the same place of residence as another subject in any AR101 study

4.3 Early Termination

4.3.1 Criteria for Early Termination

Any subject will be prematurely terminated from additional IP exposure for the following reasons:

1. Life-threatening symptoms (Consortium of Food Allergy Research [CoFAR] Grade 4; refer to the table in [Appendix 5](#)), including, but not limited to, anaphylaxis resulting in hypotension, neurological compromise, or mechanical ventilation secondary to peanut OIT dosing or any peanut food challenge
2. Severe symptoms (CoFAR Grade 3; refer to the table in [Appendix 5](#)), including, but not limited to, those that require intensive therapy (to be determined by the Investigator, but may include such interventions as intravenous (IV) epinephrine, intubation, or admission to an intensive care unit) or those that are recurrent

Any subject may be prematurely terminated from additional IP exposures for the following reasons:

1. Poor control or persistent activation of secondary atopic disease (eg, atopic dermatitis, asthma)
2. Starting any prohibited medication (Section [5.10](#)), with no alternative medications available per the prescribing doctor, unless a waiver has been obtained from the Medical Monitor, as per Section [5.7](#)
3. Pregnancy
4. Non-adherence (non-compliance) with IP dosing, as indicated by missing > 7 consecutive dosing days on any 1 occasion, or 3 consecutive dosing days on 3 or more occasions during the Up-dosing Period, as this could constitute a potential safety issue
5. Medically-indicated circumstances (eg, as part of the treatment for inter-current AEs) that require missed IP dosing for > 14 consecutive days, with the exception of the voluntary 30-day hiatus for GI-related AEs occurring at or before the 20-mg dose level

Any subject may also be prematurely discontinued from the study if:

1. The subject elects to withdraw consent from all future study activities, including follow-up.
2. The subject is lost to follow-up (ie, no further follow-up is possible because attempts to reestablish contact with the subject have failed).
3. The subject develops biopsy-documented EoE.
4. The subject's continued participation in the study is assessed by the Investigator to constitute a threat to the safety of the subject or the safe conduct of the study.
5. The subject dies.
6. The Sponsor discontinues the study.

Subjects who discontinue IP prematurely due to AEs or other safety concerns will be encouraged to continue their participation in follow-up safety assessments (see below). If a subject fails to return for scheduled visits, a documented effort must be made to determine the reason.

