Based on experience from Phase 2 study results, most acute allergic responses to dosing that are characterized by mild symptoms would be anticipated to meet the above criteria. If, however, an allergic response to dosing is characterized by mild symptoms that do not meet all of the above criteria (eg, has mild symptoms occurring in 2 or more organ systems, requires treatment with 2 doses of antihistamine or 1 dose epinephrine, shows progression in severity or distribution over time, is protracted in duration, or includes objective wheezing), then even though the allergic symptoms may be mild, the dose should be assessed to be not tolerated. If a dose elicits mild symptoms that do not fit all of the above criteria and the dose is assessed to be tolerated, then a brief explanation as to why the dose was considered tolerated must be recorded in the CRF.

Moderate symptoms: In general, if a dose elicits moderate symptoms, the dose will be assessed as not tolerated. There may, however, be rare occasions when a dose eliciting moderate symptoms could be assessed as tolerated. Generally, this would only be the case for a transient, self-limited (requiring no intervention and resolving completely) symptom occurring in a single organ system. In addition, typically the symptom would be subjective only. Any dose associated with moderate symptoms and assessed as tolerated must be accompanied by a brief explanation in the CRF as to why the dose was considered tolerated.

Severe symptoms: If a dose elicits severe symptoms, the dose will be assessed as not tolerated. Whenever a dose elicits an allergic response characterized by 1 or more severe symptoms, the crucial decision, after adequate treatment for the allergic reaction has been administered, will be to determine whether the subject should continue in the study, dosing at a reduced dose level, or be discontinued early from the study.

The determination of tolerability will decide the course of action to be taken in response to dose-related reactions (Section 6.5.3).

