6.5.5 Treatment for Reactions During the Up-dosing Period: Dose Adjustment

If a dose or dose level is assessed *as not tolerated*, the action taken will depend on the type and severity of the dose-related reaction and the Investigator's clinical judgment. Dosing must be at a dose level listed in [Table 2](#); dosing below 3 mg/day is not allowed. The following possible actions are at the Investigator's disposal and are considered in greater detail in subsequent sections (Section 6.5.5.1, Section 6.5.5.2, and [Figure 2](#)):

- Dosing the subject under medical supervision in the CRC – this is encouraged whenever there is question as to the tolerability of a dose level. It may be performed at the current dose level or at a reduced dose level, if there is already a high index of suspicion that the current dose level has not been tolerated.
- Holding dose level at current level for an additional 1 to 2 weeks before attempting dose escalation – this may be done at the discretion of the Investigator if there is concern that the current dose level has not been sufficiently well tolerated to attempt up-doing to the next dose level.
- Reducing dose by 1 or 2 dose levels and maintaining the reduced dose level for ≥ 2 - to 4-week period before attempting dose re-escalation – Generally, this should be the

action taken when a dose that has been observed in the CRC is assessed as not tolerated, if a dose elicits moderate or severe reactions that require no more than a single dose of epinephrine for treatment, or if the Investigator is convinced of the intolerability of the current dose level. In short, it should be considered the default action whenever a dose or dose level is assessed *as not tolerated*.

- Reducing dose level for less than the usual 2-week period – this may be instituted as treatment for an inter-current AE, to aid the Investigator in determining if a dose level is or is not tolerated, or if a pattern of decreased IP tolerability during menses is discerned. The level of the reduction in dose, ranging from a 1-step reduction to a 50% reduction will be at the Investigator's discretion, based on clinical judgment. The manner in which dose escalation may resume will depend on the level and the duration of the dose reduction.

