If *moderate symptoms* occur with the first dose at a new dose level, except for rare instances, the dose will be *assessed as not tolerated*. The action taken should be to have the subject return to the CRC the next day for dosing at the last tolerated dose under medical supervision. Dosing below 3 mg/day is not allowed. If this reduced dose elicits no allergic symptoms (ie, is well tolerated), the subject will continue on that daily home dose level for an additional 2 weeks. If the subject experiences mild symptoms at the reduced dose, the procedures for responding to a dose with mild symptoms should be followed (see above and Figure 2). If the subject experiences moderate symptoms at the reduced dose level, the subject should return to the CRC the next day and receive a further 1- or 2-step dose reduction (per Investigator judgment). If this reduced dose is well tolerated, it will be continued as the daily home dose for ≥ 2 weeks before re-escalation is attempted in the CRC. If the dose is not well tolerated, but elicits mild symptoms, then the treatment procedures for responding to mild symptoms should be followed (see above and Figure 2). If, however, the subject again experiences moderate symptoms at the reduced dose level, a discussion with the Medical Monitor is to ensue to reach a decision as to whether to continue the subject in the study.

In the rare instance that a dose eliciting moderate symptoms is *assessed as tolerated*, then the actions taken should be the same as for a dose with mild symptoms *assessed as tolerated*.

If *severe symptoms* occur, the action should be to treat the subject for the allergic reaction, and then, in consultation with the Medical Monitor, decide whether or not to discontinue the subject from the study. If it is determined that it is safe to allow the subject to continue in the study, the

subject should return to the CRC the next day for dosing at a 2-step reduction in dose under observation. Dosing below 3 mg/day is not allowed. If the subject tolerates the dose reduction (ie, shows no or only mild symptoms that are assessed as tolerated), then the subject is to remain at the reduced dose level for \geq 2 weeks before returning to the CRC to attempt dose re-escalation. If the subject does not tolerate the reduced dose, then the subject is to be considered an escalation failure non-responder.

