- If a reduction in dose is maintained for 8 to 14 consecutive days, then the next escalation attempted must be conducted in the clinic, and it should only be to 1 dose level above the reduced dose. If the escalation is successful, the subject should continue home-dosing for a minimum of 2 weeks, with his or her biweekly escalation schedule reset as necessary.

Doses of IP may also be withheld at the Investigator's discretion, in response to an inter-current AE. Doses withheld as part of the treatment for an AE constitute a special category of missed peanut OIT doses ([Section 6.6](#)).

6.5.6 Treatment for Reactions During the Up-dosing Period: Pharmacological and Supportive Treatments

Treatment of acute reactions should be with either an antihistamine and/or epinephrine, along with IV fluids, a beta-agonist (eg, albuterol, by inhaler or nebulizer), oxygen, and/or corticosteroids, as indicated.

Many mild acute allergic reactions can be transient and self-limiting, requiring no therapeutic intervention. Others, however, may require treatment. Generally, for mild symptoms requiring treatment, the subject should receive antihistamines.

Acute allergic reactions manifesting with moderate symptoms will generally require therapeutic intervention, although some, even moderate, symptoms may on rare occasion be so transient as to require no specific treatment. Generally, for moderate symptoms requiring treatment, the subjects should receive antihistamines and/or epinephrine, as indicated. If there is uncertainty as to the severity of the reaction, administering epinephrine would be considered the most appropriate course of action.

Generally, severe symptoms will require treatment with epinephrine at a minimum. If severe symptoms that qualify as Stage 3 anaphylaxis (defined in [Appendix 4](#)) occur at any time, dosing with IP will stop and the subject will be discontinued from the study as an escalation failure non-responder.

Antihistamines

If a subject receives antihistamines only, the dose escalation can be continued. If epinephrine is administered, then a different course of action is to be taken.

Epinephrine - General

Any reaction to IP (in clinic or at home) that requires more than 2 doses of epinephrine will halt all further dosing of IP for the individual. The subject will be asked to return to the CRC 14 days following the last dose of IP to undergo an Early Discontinuation Visit (Section [6.3.6](#)).

Epinephrine - Clinic

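### Read literally, Protocol 4.3.1 stops study product after any severe (CoFAR Grade 3) reaction, while the dosing sections let a child with a first such reaction after initial escalation continue at a reduced dose, and nothing says which rule governs

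*Protocol*

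**What the plan says.** **The termination rule.** Section 4.3.1 has two lists about stopping study product. The first is mandatory: "Any subject will be prematurely terminated from additional IP exposure for the following reasons". The second covers reasons for which a subject may be stopped. Severe symptoms, defined as CoFAR Grade 3, are item 2 of the mandatory list, "including, but not limited to, those that require intensive therapy"; the item then also names symptoms that recur.

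**The dosing rules after initial escalation.**
- Section 6.5.2: after a severe reaction has been treated, the decision is to "determine whether the subject should continue in the study, dosing at a reduced dose level, or be discontinued early from the study".
- Section 6.5.5: a reduction of 1 or 2 dose levels is generally the action "if a dose elicits moderate or severe reactions that require no more than a single dose of epinephrine for treatment".
- Section 6.5.5.1: once the reaction has been treated, the investigator is to act as follows: "in consultation with the Medical Monitor, decide whether or not to discontinue the subject from the study". Going on with dosing depends on a judgment of safety. Where that judgment is favorable, the instruction for the following dose reads: "subject should return to the CRC the next day for dosing at a 2-step reduction in dose under observation".

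**The other stops.** Section 6.3.3 calls for discontinuation when severe symptoms include hypoxia, hypotension or altered mental status, or when intensive therapy is given. Section 6.5.6 stops dosing for Stage 3 anaphylaxis and after more than two epinephrine doses for one reaction. Section 7.9.2 lists individual stopping rules; a first Grade 3 reaction is not among them.

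**The concern.** These rules decide whether a child who has just had a severe allergic reaction is given the allergen again. One site can stop a child for good under 4.3.1. Another can re-dose a child with the same reaction under 6.5.5.1. Both can cite the protocol. The second site also departs from the literal text of 4.3.1, so a monitor could record a deviation for following the dosing algorithm.

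The main stake is consistent and safe handling of children. The statistical stake is small: discontinuation of dosing due to adverse events is a secondary endpoint, summarized descriptively, and its meaning would depend partly on which section a site followed.

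**Working it through.** The plan states no figure to reproduce on this point. The check is a comparison of texts, with a short calculation for scale.

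**Step 1. Is 4.3.1 mandatory for every Grade 3 reaction?** Literally, yes. The list containing item 2 is set apart from the discretionary list that follows, and the wording of item 2 makes intensive therapy and recurrence examples, not conditions.

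**Step 2. Do the two sets of rules use different severity scales?** No. Section 6.5.1 says that its definitions were built to be consistent with CoFAR, and Section 7.4 grades allergic reactions by CoFAR.

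**Step 3. Is there a child to whom both rules apply?** Take throat tightness with hoarseness, graded severe by the investigator and treated in clinic with one epinephrine dose, with no hypoxia, hypotension or change in mental status.

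| Text | Treatment of this case |
|---|---|
| 6.5.1 | Severe |
| Appendix 5 | A listed Grade 3 symptom |
| Appendix 4 | Hoarseness is Stage 2, so not by itself Stage 3 |
| 4.3.1 item 2 | Must stop |
| 6.3.3 and 6.5.6 severity stops | Not triggered |
| 6.5.2, 6.5.5, 6.5.5.1 | May continue at a reduced dose |

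The single epinephrine dose is not unusual: Section 6.5.6 says "Generally, severe symptoms will require treatment with epinephrine at a minimum". After one clinic dose of epinephrine, that section bars further product at the visit, cuts the next dose by 2 levels, gives it in clinic, and lets biweekly escalation go on. Epinephrine use triggers that rule, not severity, so it does not settle the conflict.

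**Step 4. Where does the conflict apply?** Only after initial escalation. During initial escalation, 6.5.4 ends dosing for severe symptoms at any dose, in line with 4.3.1. Section 6.3.5 ends the Up-dosing Period at the first 300 mg visit, so the 300 mg weeks must be covered by name in any repair.

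**Step 5. What about reactions at home?** Section 6.5.3.1 brings the child to clinic the next day for the next dose and does not mention the Medical Monitor. Section 6.5.5.2 refers to the 6.5.5 procedures, and 6.5.5 points on to 6.5.5.1. Consultation can be reached by that chain but is not stated.

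**Step 6. Does any text give precedence?** None was found in the protocol or SAP.

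**Step 7. Scale.** Inputs: up to 500 subjects randomized 2:1 (Section 3), and severe symptoms expected in under 1% of subjects on the basis of earlier oral immunotherapy studies (Section 1.4.1).

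- AR101 subjects: 500 × 2/3 = 333.
- Expected number with a severe reaction: 333 × p.
- p = 1%: 3.33. p = 0.5%: 1.67. p = 0.1%: 0.33.

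The 0.5% and 0.1% rates are illustrative values below the protocol's 1%. That 1% is an expectation, not a cap. With a true rate of exactly 1%, X ~ Binomial(333, 0.01) gives P(X > 3) = 0.43 and a 95th percentile of 7 children (7/333 = 2.1% of the arm).

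Only severe reactions after initial escalation that miss every existing stop fall in the conflict. The documents do not give that share, so the counts above are upper figures for the number of conflict cases at each rate.

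**The case against.** The strongest case on the other side is that one line is loosely drafted and the intent is clear. If every first Grade 3 reaction ended dosing, a severe reaction could hardly recur on study product, and the mention of recurrence in item 2 would do almost no work. Sections 6.5.2, 6.5.5 and 6.5.5.1 all allow continuation, and 6.3.3 and 6.5.6 are compatible with them. That reading is probably what the authors meant. It lowers the severity of the point, but it does not remove the contradiction: item 2 says that its examples are not limits, and no text adopts the narrower reading.

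The safeguards also count. Section 6.5.5.1 requires treatment, consultation, a judgment that continuing is safe, a 2-step reduction and observed dosing. A child who does not tolerate the reduced dose is an escalation failure. Two epinephrine doses for one event mean at least 6 weeks at a reduced dose; more than two end dosing. Section 6.5.5 obliges the investigator to discontinue a child whose health could be jeopardized. These limit the risk, but none says which rule governs.

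Figure 2, the up-dosing schematic, was not in the text available for review. It may show the intended rule; it would not remove the conflicting text.

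A reader might infer that the protocol permits unchecked re-dosing the day after a severe reaction. The conditions in 6.5.5.1 do not support that. A reader might also infer a gap in initial escalation, because 6.3.1 lets a child with dose-limiting symptoms only at 6 mg return on Day 2. Section 6.5.4 already settles that for severe symptoms.

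**Conclusion.** The contradiction is real and should be fixed. On the literal text, a child with a first Grade 3 reaction after initial escalation, without intensive therapy, Stage 3 features or more than two epinephrine doses, must stop under 4.3.1 and may continue under 6.5.5.1.

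Few children are affected. At the protocol's expected rate, fewer than about 3.3 AR101 subjects would have any severe reaction, and the conflict cases are a subset of those. The expected effect on the descriptive discontinuation endpoint is therefore below about 1 percentage point of the AR101 arm (3.33/333). This assumes full enrollment of 500 and that the under-1% expectation carries over to this trial.

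A reader might go further and conclude that the stricter rule must prevail, or that the trial cannot safely run until this is settled. The documents support neither. They point, if anything, to the narrower rule as the intent, and the safeguards contain the risk in the meantime. Whether any Grade 3 reaction should end dosing is a clinical choice for the sponsor and the DSMC.

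**What to change.** Reword 4.3.1 item 2 along these lines:

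> *Any severe (CoFAR Grade 3) symptoms during initial escalation (Section 6.5.4); at any time after initial escalation, including 300 mg dosing, Grade 3 symptoms that require intensive therapy, that are recurrent, or that include hypoxia, hypotension, change in mental status or Stage 3 anaphylaxis. After any other Grade 3 reaction, in clinic or at home, no further IP is given until the Medical Monitor has been consulted under Section 6.5.5.1.*

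Then:
- Add a pointer to this rule in 6.5.2, 6.5.3.1, 6.5.5 and 6.5.6.
- In 6.5.5, state that the reduction after a severe reaction is 2 dose levels, so that it agrees with 6.5.5.1.

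If the sponsor and DSMC prefer to stop after any Grade 3 reaction, they can keep item 2 and remove the option to continue from the dosing sections. Either way, one rule should stand.

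The cost is a protocol amendment with IRB/EC approval and health-authority submission (Section 10.1) and a check of the consent and assent forms (Section 10.2). The rewording adds no scheduled visits, tests or subjects. For home reactions it makes explicit a consultation that can now be reached only by cross-reference.
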